1.0 Background

Great efforts are undertaken in the perioperative period to avoid infection, a major cause of morbidity and mortality. Still, infection rates can range from 0.6% to 5%, depending on the type of surgery performed.¹ Studies in the orthopaedic literature have shown that organisms usually characterized as more indolent, such as *P. acnes*, a known skin pathogen, cause surgical site infections following shoulder surgery despite proper preoperative surgical preparation.² Matsen et al. hypothesized that *P. acnes* infections do not originate from the superficial epidermis, but from the dermal layer, which may be expected as *P. acnes* is known to reside in the sebaceous glands and hair bulbs.^{2,3}

Lee et al. showed a 70% growth rate of *P. acnes* despite the application of Chloraprep prior to sampling, contradicting previous studies that found only 7% growth in the superficial layer of the skin using the same skin preparation.^{4,5} However, this study was limited as it failed to utilize a control group and only investigated one preparatory technique. Meanwhile, there remains to date no study investigating the effect of topical treatments in eradicating *P. acnes* within the dermal layer. The purpose of this study is to investigate how specific topical treatments affect growth in the dermal layer.

2.0 Objective and Purpose

1. What is the prevalence of Propionibacterium in the dermal layer following topical treatments?
2. Does the type of topical treatment used affect the prevalence of Propionibacterium in the dermal layer?

Primary Outcome:

Positive growth of Propionibacterium acnes on bacterial culture.

Secondary Outcomes:

Positive hemolysis on brucella agar.

3.0 Study Design

Twelve healthy volunteers who are over the age of 18 will be consented to participate in our study. Those individuals with active acne or those who received a course of antibiotics in the last month will be excluded. The subject's upper back will be sectioned into quadrants above the scapular spine, which will be each assigned a different topical treatment: clindamycin alone, benzoyl peroxide alone, clindamycin plus benzoyl peroxide, and a control, with no topical application. Each application will be applied twice daily for 3 consecutive days. Randomization will be performed using a random number generator to draw numbers 1-4 in order to designate a topical treatment to each quadrant. Quadrants will be labeled with surgical markers to ensure the correct treatment is applied. Research subject will be trained on application using a mirror with the research staff during recruitment.

A 3-mm dermal punch biopsy specimen will be obtained at each site using a commercially available kit after prepping with isopropyl alcohol and sterile injection of local anesthesia with 2% lidocaine with epinephrine. The biopsy sites will be covered with sterile gauze and allowed to heal without closure. Unfortunately, due to procedural limitations, the dermal layer of the skin cannot be accessed without penetrating the epidermis. Thus even separating the dermis from the epidermis is not helpful because the dermis will have been contaminated from potential pathogens from the epidermis during the biopsy procedure.

A total of four punch biopsies will be obtained from the subject's back; one for each of type of topical treatment and the control. The four punch biopsy specimens will then be cultured for *P. acnes*, with serotyping, and held for 21 days to assess for growth. Assessment of growth will be made the USC Microbiology Lab, who will be blinded to the treatment condition.

Pipettes will be used to inoculate the fluid onto the following media: blood agar, chocolate agar, brucella agar, and brain heart infusion broth. This same culture technique was used by Lee et al, in their published study investigating *P. acnes* levels in the dermis of the skin.⁴ In order to determine hemolytic subtype, the samples will also be tested on Brucella Blood agar, as described by Wright et al.⁶

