6.0 Sample Size

We will recruit participants until there are 12 total subjects.

Power Analysis:

Data from previous studies were used to estimate that 70% of cultures will grow positive for *P. acnes* with no therapy.⁴ For a clinically meaningful response, we would expect only 5% of cultures to grow positive for *P. acnes* following treatment. Thus, for an alpha of 0.05 and power of 80%, we would need a minimum of 12 biopsies per treatment group to have adequate power, based on a McNemar test for paired proportion comparison.

Sample Size:

We will recruit a minimum of 12 total subjects to achieve adequate power. Because each patient is receiving 4 biopsies, there will be a total of 48 samples.

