8.0 Assessment of Efficacy and Safety

Side effects and toxicities to be monitored:

1. Anaphylactic reaction: symptoms include flushing, itching, swelling, difficulty breathing, and fainting.
2. Nerve Weakness
3. Infection
4. Fever
5. Swelling
6. Abscess formation
7. Dizziness
8. Visual Disturbances
9. Headache
10. Nausea
11. Seizure
12. Diarrhea
13. Abdominal pain
14. Arrhythmia (abnormal heart rhythm)

Because only 2-4 mL of 2% lidocaine with epinephrine will be used there will be no longterm follow-up for these subjects.

The principal investigator is the individual responsible for monitoring and reporting the occurrence of adverse events throughout the study. Subjects will be monitored throughout the study. Subjects will be taken off the study participation if they experience any side effects. USC orthopaedic staff will also monitor for any un-anticipated events. Anticipated adverse events are discussed in the Informed Consent Form for this study.

The research team will follow the IRB Adverse Even Policy on mandatory reporting of Serious Adverse Events (SAEs), and we will also report them immediately both orally and in writing to the IRB Program Director within 24 hours of occurrence or recognition.

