10.0 Criteria for Evaluation and Endpoint Definitions

All eligible subjects who meet inclusion criteria will be included in the analysis.

The primary outcome will be positive growth of *P. acnes* on culture. Secondary outcome will be subtyping based on hemolysis. The USC Microbiology lab assess the samples and will be blinded to treatment condition. They will only receive the participant ID and corresponding treatment number.

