11.0 Data Collection and Monitoring

Protections against risks:

All key personnel have completed courses on protection of human subjects.

Protections against biomedical risks:

Only qualified trained orthopaedic surgeons will be performing the biopsies using sterile technique.

Confidentiality:

To minimize this risk, only the investigators will have access to all data containing personal information. All data will be locked in the PI's office and/or lab. To preserve confidentiality, immediately after enrollment the subjects will be assigned a code by which each research subject will be identified for further analysis.

Data management:

All the study data will be collected by the research team and recorded on data collection form, found in section 16.0. Immediately after enrollment each subject will be assigned a code by which each research subjects will be identified for further analysis to avoid identification by non-qualified individuals.

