12.0 Statistical Considerations

Statistical Analysis:

Primary outcomes will be treatment comparisons on the percentage of subjects with positive cultures for *P. acnes*. Primary outcomes will be analyzed using generalized estimating equations to account for the within-subject correlated outcomes, as all 4 interventions will be evaluated on each subject. Given the dichotomous outcome (presence/absence of *P. acnes*), the analysis will use a logistic model (binomial random outcome with a logit link function). Three indicator treatment variables will be specified (e.g., clindamycin, benzoyl peroxide, clindamycin plus benzoyl peroxide; with lidocaine as the referent group). A 3df overall test of the treatment indicators will test for any differences in positivity for *P. Acnes* among the treatments; pairwise comparisons among the treatments will adjust for multiple comparisons. A two-tailed statistical test will be performed, testing at an alpha of 0.05. Analyses will also be performed based on hemolytic subtypes.

Power Analysis:

Data from previous studies were used to estimate that 70% of cultures will grow positive for *P. acnes* with no therapy.⁴ For a clinically meaningful response, we would expect only 5% of cultures to grow positive for *P. acnes* following treatment. Thus, using a McNemar test for paired proportion comparison, with an alpha of 0.05 and power of 80%, we would need a minimum of 12 biopsies per treatment group to have adequate power.

Sample Size:

We will recruit a minimum of 12 total subjects to achieve adequate power. Because each patient is receiving 4 biopsies, there will be a total of 48 samples.

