16.0 Data Collection Sheet

Pt Code	Age	Sex	Biopsy group (Control vs. Clindamycin vs. Benzoyl Peroxide vs. Clindamycin and Benzoyl Peroxide)	Positive Culture	Hemolytic Subtype	Adverse Events?

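### Does the treatment-to-quadrant randomisation need a stated per-subject draw, a quadrant column and Latin-square balance?

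*Combined protocol and SAP*

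**What the plan says.** Section 3.0 Study Design sets up complete within-subject blocks: "The subject's upper back will be sectioned into quadrants above the scapular spine, which will be each assigned a different topical treatment". The assignment rule follows: "Randomization will be performed using a random number generator to draw numbers 1-4 in order to designate a topical treatment to each quadrant". The quadrants are then marked on the skin so that the right product goes on the right area. No section describes blocking or balance over quadrants.

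Section 11.0 sends the data to one form: "All the study data will be collected by the research team and recorded on data collection form, found in section 16.0". For each biopsy, that form (section 16.0) has the field "Biopsy group (Control vs. Clindamycin vs. Benzoyl Peroxide vs. Clindamycin and Benzoyl Peroxide", with columns for code, age, sex, culture result, hemolytic subtype and adverse events. It has no quadrant column. Section 10.0 says of the laboratory: "They will only receive the participant ID and corresponding treatment number".

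Section 12.0 specifies a logistic GEE with treatment terms only: "Three indicator treatment variables will be specified". Section 6.0 gives the size: "We will recruit a minimum of 12 total subjects to achieve adequate power".

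**The concern.** The quadrant is the randomised unit, yet three things about it are unwritten: how often the draw is made, how conditions spread over quadrants, and where each quadrant's assignment is recorded.

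If a single draw served all 12 subjects, treatment and quadrant would be fully confounded, and any difference between sites would pass for a treatment effect. If the draw is made per subject, chance imbalance remains. With 12 subjects, one condition can easily miss a quadrant. Subjects apply the products themselves with a mirror, so a difference between positions is conceivable. Without a quadrant column, neither the executed randomisation nor a position effect could be examined from the data form. Since 12 is a multiple of 4, Latin squares would remove the imbalance with no extra subject or biopsy.

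**Working it through.** **The plan's own figure.** Inputs from sections 6.0 and 12.0: 70% against 5%, two-sided alpha 0.05, power 80%, McNemar. The within-pair correlation is not given; independence is assumed. The discordant probabilities are 0.70 x 0.95 = 0.665 and 0.30 x 0.05 = 0.015. Exact McNemar power is 0.799 with 11 subjects and 0.861 with 12, so the stated 12 reproduces.

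**Chance imbalance under per-subject draws.** Each condition-quadrant count is Binomial(12, 0.25), with mean 3.
- A given cell is empty: 0.75^12 = 0.032.
- A given cell has 6 or more subjects: 0.054.
- Control misses some quadrant: 4(0.75^12) - 6(0.5^12) + 4(0.25^12) = 0.125.
- Any of the 16 cells is empty: about 40% (simulation).

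These figures describe spread, not bias. Each condition is equally likely to fall on each quadrant, so the expected treatment difference is unaffected.

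**What balance does to the true variance.** Assume two quadrants with positivity h and two with l, outcomes independent given quadrant, and no treatment effect. Let g = h - l, and let v be the mean of h(1-h) and l(1-l). Two conditions in one subject fall in different halves with probability 2/3. For the mean difference over 12 subjects:
- Per-subject draws: variance = [2v + (2/3)g²]/12.
- Latin squares: variance = 2v/12.

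With h = 0.85 and l = 0.55 (logit shift about +/-0.75), v = (0.1275 + 0.2475)/2 = 0.1875 and g² = 0.09.
- Draws: (0.375 + 0.060)/12 = 0.03625, SD 0.190.
- Squares: 0.375/12 = 0.03125, SD 0.177.

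With h = 0.78 and l = 0.62 (shift +/-0.4), v = 0.2036 and g² = 0.0256, giving SDs of 0.188 and 0.184.

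**What the planned analysis would report.** Every subject has all four conditions, so the treatment-only GEE reduces to the arm proportions with a sandwich covariance built from between-subject variation. For a difference, that variance is the sum of squared deviations of the 12 within-subject differences, divided by 12². At h = 0.85, l = 0.55:
- Draws: expected sum = 11 x 0.435 = 4.785; 4.785/144 = 0.0332; SE 0.182.
- Squares: expected sum = 12 x 0.435 - 0.375 = 4.845; 4.845/144 = 0.0336; SE 0.183.

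With divisor 11 x 12 in place of 144, the pair is 0.190 and 0.192. In both forms the quadrant variation stays in the estimated variance because the model does not remove it. Confidence intervals would be no shorter.

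**Power, per-subject draws against Latin squares** (simulation, 150,000 trials per scenario, all site effects assumed):

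| Logit site shift | GEE 3-df, 70% vs 30% | Exact McNemar, 70% vs 5% |
|---|---|---|
| none | 0.496 / 0.496 | (no site effect, no gain) |
| +/-0.4 | 0.491 / 0.489 | 0.861 / 0.861 |
| +/-0.75 | 0.477 / 0.474 | 0.856 / 0.867 |
| +/-1.5 (extreme) | 0.444 / 0.434 | 0.850 / 0.877 |

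At 70% against 30% and +/-0.75, exact McNemar power falls from 0.29 to 0.27. The GEE cannot be compared at 70% against 5%, because about 90% of simulated trials have an arm with 0 or 12 positives under either scheme. If quadrants differ only in how well subjects reach them (shift +/-0.75 in treated quadrants only), the SD at 70% against 5% is 0.146 under both schemes.

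**Reading of the draw.** Section 3.0 speaks of one subject's back, divides it, assigns a different treatment to each part, and then names the draw. In that sequence the draw belongs to the subject. A draw shared by all would, at +/-0.75 and with no treatment effect, give a 29-point difference between two conditions in different halves (probability 2/3) and GEE null rejection of 26%. Those figures apply only to that unlikely reading.

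**The case for a change.** The strongest case for acting is cost. A sentence on the per-subject draw would exclude the one damaging reading. A quadrant column would let the executed randomisation be checked, and quadrant may not be recoverable later if it is not kept. Three Latin squares need no more than the planned 12 subjects and 48 biopsies, and at +/-0.75 they cut the true variance by about 14% (1 - 0.03125/0.03625). GEE null rejection also moves closer to nominal there, from 6.8% to 5.1%.

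The facts stand: the sentence and the column are absent. The variance reduction is also real if quadrants differ, but it does not reach the planned analysis, which has no quadrant terms. The lower null rejection comes from an analysis that ignores the balance and so turns conservative, which happens to offset small-sample liberalism of the sandwich variance. At +/-1.5 it drops to 2.3%. Balance also depends on completion, and section 8.0 says: "Subjects will be taken off the study participation if they experience any side effects". Most of the true-variance gain survives small losses (null SD at +/-0.75 of 0.199 against 0.187 with one subject lost), so withdrawals are not the deciding point. An assignment list must exist in any case, since the skin is marked and each biopsy is labelled with its group. The column would serve audit and a possible sensitivity check, neither of which the plan relies on.

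**Conclusion.** No change follows. Under the natural reading, each subject has an independent random assignment of four conditions to four quadrants. That is unbiased and valid, and the planned 12 subjects reproduce with exact McNemar power of 0.861 under independent pairs. The unstated repetition of the draw and the missing quadrant field are gaps that a competent team fills without altering any planned estimate or test.

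Latin squares are a design preference. Under the planned treatment-only GEE they give no shorter intervals (SE 0.182 against 0.183 at +/-0.75) and no gain in overall power at 70% against 30% (differences of 0 to 0.010, none favouring squares). For exact McNemar, which is the sample-size test and not the primary analysis, they add 0 to 3 points at 70% against 5%, with the 3 only at an extreme site effect.

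The conclusion rests on the per-subject reading and on the model staying without quadrant terms. All site effects used are assumptions. Within-subject independence given quadrant is also assumed; adding a subject random effect (SD 1) at +/-0.75 leaves GEE power at 0.554 against 0.552.

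### Masking is described only for the laboratory: nothing masks specimen collection or fixes punch point and biopsy order, and the laboratory's treatment number may group samples by arm

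*Combined protocol and SAP*

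**What the plan says.** Section 3.0 Study Design divides the upper back into four quadrants. Three receive a gel and the fourth is described as "and a control, with no topical application". On allocation it says: "Randomization will be performed using a random number generator to draw numbers 1-4 in order to designate a topical treatment to each quadrant". Marks on the skin guide application: "Quadrants will be labeled with surgical markers to ensure the correct treatment is applied". The subject is trained to apply the gels ("Research subject will be trained on application using a mirror with the research staff during recruitment"), and the schedule is "Each application will be applied twice daily for 3 consecutive days".

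On collection, the same section says: "A 3-mm dermal punch biopsy specimen will be obtained at each site using a commercially available kit after prepping with isopropyl alcohol". Section 11.0 adds: "Only qualified trained orthopaedic surgeons will be performing the biopsies using sterile technique". Section 3.0 also concedes that the dermis cannot be reached without passing through the epidermis, and that the specimen is contaminated on the way.

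Sections 3.0 and 10.0 both blind the microbiology laboratory. Of the laboratory, Section 10.0 says: "They will only receive the participant ID and corresponding treatment number". No other role is described as masked.

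**The concern.** The primary outcome is presence or absence of growth from one small specimen per site. By the plan's own account, organisms from the surface can enter that specimen during the biopsy. How the site is prepared, where in the quadrant the punch falls, and when in the sequence it is taken could all affect whether anything grows. An operator who knows which quadrant is the control could handle the four sites differently without meaning to. A masked reader cannot undo that, and the difference would be counted as a treatment effect. The bias could run either way: it could create a difference or hide one.

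The laboratory safeguard has a gap of its own. If numbers 1 to 4 stand for the same treatments throughout, the 48 samples arrive sorted into four groups of 12, and a single disclosure decodes all of them.

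**Working it through.** **Step 1: which stages are protected.**

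| Stage | What the plan fixes | What it leaves open |
|---|---|---|
| Allocation (3.0) | Random assignment of treatments to quadrants within each subject | Who holds the list; whether the numbering is the same for every subject |
| Skin labels (3.0) | That they exist, and their purpose | What they show; whether they are legible or removed at biopsy |
| Collection (3.0, 11.0) | Punch size, kit, isopropyl alcohol, anaesthetic; surgeons take the biopsies | Masking of the operator; punch point; order; prep time; who preps and who labels specimens |
| Culture reading (3.0, 10.0) | Laboratory blinded | Whether the treatment number is a constant code |

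The stage at which the plan admits contamination is a stage for which it describes no masking.

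**Step 2: the plan's own figure.** Sections 6.0 and 12.0 give 70% positive without therapy, 5% after treatment, alpha 0.05 (two-sided in 12.0), power 80% and a McNemar test. Within-subject correlation is not given, so independence is assumed.

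- Discordant cells: p10 = 0.70 × 0.95 = 0.665; p01 = 0.30 × 0.05 = 0.015.
- ψ = p10 + p01 = 0.680; d = p10 − p01 = 0.650.
- n = [1.96√ψ + 0.8416√(ψ − d²)]² / d² = 9.88.
- With continuity correction: (n/4)[1 + √(1 + 2/(n·d))]² = 11.37, rounded up to 12.

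The stated 12 reproduces. The present point concerns bias and leaves that number unchanged.

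**Step 3: how large a handling effect would have to be.** The documents give no handling effect, so the figures below are illustrative. Suppose no treatment works, true positivity is 70% at every site, and collection lowers recovery at treated sites to q. Under independence p10 = 0.70(1 − q) and p01 = 0.30q. For b and c discordant pairs with m = b + c, the exact two-sided p-value is 2·Σ C(m,i)/2^m, summed over i from 0 to min(b,c) and capped at 1. With 12 subjects, significance at 0.05 needs a split such as 6–0 (2/64 = 0.031), 8–1 (20/512 = 0.039) or 10–2 (158/4096 = 0.039). The multinomial probabilities of all significant splits, in both directions, are added. Each q was also run with an assumed within-subject correlation of 0.3, and with the uncorrected McNemar test.

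| q | Loss (points) | p10, p01 (independent) | Exact, independent | Exact, corr. 0.3 | Uncorrected, independent | Uncorrected, corr. 0.3 |
|---|---|---|---|---|---|---|
| 70% | 0 | 0.21, 0.21 | 0.9% | 0.3% | 5.1% | 4.1% |
| 60% | 10 | 0.28, 0.18 | 2.2% | 1.1% | 7.7% | 8.3% |
| 50% | 20 | 0.35, 0.15 | 6.3% | 4.8% | 15.1% | 20.0% |
| 40% | 30 | 0.42, 0.12 | 14.9% | 14.4% | 27.7% | 39.6% |

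These are rates per comparison, without multiplicity adjustment. The planned logistic GEE analysis in 12.0 was not simulated.

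**The case against.** The plan already standardises much of collection. Every site gets the same punch, kit, antiseptic and anaesthetic, and trained surgeons work under sterile technique. Treatments are randomised to quadrants within subjects, so an order that depends only on position does not systematically favour any treatment. The endpoint is laboratory growth, not the operator's judgement. With the exact test, the false-positive rate passes the nominal 5% only at a loss of about 20 points, which is large. Neutral codes could also make it harder for subjects to put the right gel in the right place, which is what the labels are for.

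Most of this stands as a limit on severity. It does not close the gap: randomising quadrants does not protect against handling that depends on knowing the allocation, and punch point, order and prep time remain open. The application worry is met by putting the same position code on the tube as on the skin, so that the subject matches codes and needs no lookup sheet.

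A reader might go further and infer that the marks name the treatment, are still legible at biopsy, and are seen by a surgeon who preps, chooses the spot and handles the specimens, so that collection is unblinded. The documents do not say this. The wording of the labels and their state on the biopsy day are not given. Section 11.0 says only that surgeons take the biopsies. A number on the skin would not reveal the allocation to someone without the key, and the plan does not say who holds it.

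**Conclusion.** The point holds as a gap in the design: masking is described for the laboratory alone, the skin labels may reveal allocation to the operator, and punch point and biopsy order are not set in advance, although the plan accepts contamination during biopsy. The laboratory's masking is weaker than it appears only if treatment numbers are constant across subjects, which the plan leaves unclear; it does not follow that the laboratory is unblinded.

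The size of the bias is unknown. The illustrative 2.2%, 6.3% and 14.9% for losses of 10, 20 and 30 points (0.9% with none) rest on an assumed handling effect, independent sites, 70% true positivity everywhere and the exact McNemar test. The uncorrected test is more sensitive, at 7.7% for a 10-point loss. Against the 65-point difference the trial is sized for (70% − 5%), modest handling effects would matter mainly if the true treatment effect were small or absent. This is a worthwhile low-cost improvement. It does not invalidate the design or change the sample size.

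**What to change.** Amend Sections 3.0, 10.0 and 16.0 as follows.

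- Mark quadrants with position codes only (for example A to D), and label each subject's gel tubes with the matching code.
- Have an existing team member who does not take biopsies hold the subject-specific key linking position to treatment.
- Set the punch point within the quadrant and the order of the four biopsies by position in advance, and apply the prep already stated in the protocol identically at every site.
- Send specimens labelled with participant ID and position code in place of the treatment number. Record the position code on the data collection sheet, and add the treatment from the key after culture results are final.
- State in the protocol which roles are masked and which are not.

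The cost is protocol wording, some relabelling and a key to keep. No subjects or procedures are added, and no extra staff provided the team includes someone who does not take biopsies; the documents do not describe staffing. Masking will still be incomplete: the subject knows which quadrant received no gel, and residue or a skin reaction may show at treated sites. Fixing punch point and order limits what an operator who guesses the allocation could do differently.
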